10.2 Lesion Photography

Lesion photography will be performed on subjects who consent, with minimum 80% of total study panel.

10.2.1. Digital Photography

Photographs will be taken prior to treatments with study product and at every follow-up visit in order to document treatment effect. Site personnel will be thoroughly trained in the photographic equipment and techniques before study start.

Subjects will be carefully positioned under controlled settings (e.g., room, lighting, background, etc.) to ensure standardized photography. Digital photography will be taken of the lesion per subject.

Protocol GLI.04.US.SL.035

CONFIDENTIAL

10.2.2. Macroscopic Imaging

Macroscopic imaging procedure will be performed using Visioscan® VC 20plus at Baseline, Week 2, 4, and 8, at Site 2 only. Images will be taken of each subject's lesion at the same location.

Prior to imaging procedures, clinic personnel will ensure that subjects have clean skin on the lesion area as described in the study procedures. Subjects will be carefully positioned for each photography.

Visioscan® VC 20plus (Courage + Khazaka electronic GmbH, Koln, Germany) is a UVA-light video camera with high resolution to study the skin surface directly. The image shows the structure of the skin and the level of skin texture. The imaging area is 10 mm x 8 mm displayed in 255 pixels. The Visioscan software will be used to calculate the analyze the images for skin roughness and smoothness. Images can be displayed in 2D and 3D format.

10.2.3. Capacitance Imaging

Capacitance imaging procedure will be performed using MoistureMap MM 200 at Baseline, Week 2, 4, and 8, at Site 2 only. Images will be taken of each subject's lesion at the same location.

Prior to imaging procedures, clinic personnel will ensure that subjects have clean skin on the lesion area as described in the study procedures. Subjects will be carefully positioned for each photography.

MoistureMap MM 200 (Courage + Khazaka electronic GmbH, Koln, Germany) features a sensor based on capacitive-touch imaging technology with hardened surface. The sensor gives graphical information on the near surface hydration distribution and the micro-topography of skin and other tissue which are quantitatively assessed. The imaging area is 1.8 mm x 1.28 mm displayed on a scale of 255-pixel level, showing evenness of hydration distribution.

10.3 Subject Questionnaire

10.3.1. Quality of Life Questionnaire

Subjects will be asked about their life quality by completing a QoL questionnaire at Baseline and Week 8, as described in Appendix II.

10.3.2. Self-Assessment Questionnaire

Subjects will be asked about their perception, satisfaction, and preference with each study treatment using a self-assessment questionnaire at Week 2, 4, and 8, as described in Appendix III.

11. SAFETY ASSESSMENTS

Safety assessments for this study include:

1. Tolerability assessment

Protocol Version 02: 29 January 2024

This document contains confidential, proprietary information.

Protocol GLI.04.US.SL.035

CONFIDENTIAL

2. An evaluation and an interview of the subjects at each follow-up visit to obtain information about any medical occurrence that meets the definition of an AE.

11.1 Tolerability Assessment

Tolerability assessment will be performed by the Investigator (dryness) and by subjects (burning/stinging and itching) using a 4-point analog scale (with half-point scores used as necessary to better describe the clinical condition). Investigator and subjects will grade the degree of irritation of target lesion areas, at Baseline, Week 2, 4, and 8.

Table 4. Tolerability Scales

Score	Grade	Description
Itching: as reported by the subject within the last 24 hours		
0	None	No itching
1	Mild	Slight itching, not really bothersome
2	Moderate	Definite itching that is somewhat bothersome
3	Severe	Intense itching that may interrupt daily activities and/or sleep
Dryness: as assessed by the investigator		
0	None	No dryness
1	Mild	Slight, but definite roughness
2	Moderate	Definite roughness
3	Severe	Marked roughness
Burning/Stinging: as reported by the subject within the last 24 hours		
0	None	No burning
1	Mild	Slight burning sensation; not really bothersome
2	Moderate	Definite warm, burning that is somewhat bothersome
3	Severe	Hot burning sensation that causes definite discomfort and may interrupt daily activities and/or sleep

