Exclusion criteria:	
The presence of any of the following exclusion criteria excluded a subject from enrollment in the study:
 
 1. Pregnant, breastfeeding, or planning pregnancy during the course of the study. 2. Subjects with any known allergies or hypersensitivity to any cosmetics, personal care products, and/or fragrances. 3. History of cancer within the past 5 years 4. History or presence of any skin condition/disease, besides plaque psoriasis, that might interfere with the diagnosis or evaluation of study parameters at the discretion of the investigator. 5. Planning on having surgeries and/or invasive medical procedures during the course of the study 6. Treatment with chemotherapy, immunosuppressive agents, prescription corticosteroids for psoriasis, immunomodulatory therapy (e.g., monoclonal antibodies or antiviral treatment for human immunodeficiency virus or hepatitis C) 7. History or presence of any medical condition that, in the opinion of the Investigator, would make the subject unsuitable for inclusion (e.g., a chronic, relapsing, or hereditary disease that may interfere the outcome of the study). 8. Other condition preventing the subject from entering the study in the Investigator's opinion, (e.g., subjects failing baseline assessments, subjects not likely to avoid other treatments in the treated areas, subjects anticipated to be unavailable or incapable of understanding the study assessments or having unrealistic expectations of the treatment result). 9. Study site personnel, close relatives of the study site personnel (e.g., parents, children, siblings, or spouse), or employees and close relatives of employees at the Sponsor company. 10. Participation in any interventional clinical study within 30 days of screening or planning to participate in another interventional clinical research study while enrolled in this trial.

Investigational Products:	Cetaphil® Moisturizing Cream Cetaphil® Gentle Skin Cleanser Cetaphil® Daily Facial Moisturizer SPF 35 (supporting product)
Treatment Area / Treatment Regimen / Mode of Administration	Step 1: clean the skin with the study cleanser once daily. Step 2: with clean dry hands, apply the study moisturizing cream to the lesion areas. The study moisturizing cream will be applied at least twice daily, in tandem with prescription psoriasis treatment, following the provided instructions. Subjects may apply the test product more frequently as needed.

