5. OVERALL STUDY DESIGN

[figure not shown]
This is a multi-center, open-label, in-use study.

Subjects will report to the site at Baseline (day 0) visit, will be given an informed consent form, HIPAA form, photography release form, and medical history form to complete.

Subjects will be screened on the basis of the selection criteria for study qualification. Eligible subjects will be assessed at Baseline visit and instructed to start applying the skincare products to the assigned side of the body based on the pre-determined randomization.

Subjects to return to the site at Week 2 (± 3 days), Week 4 (± 5 days), and Week 8 (± 5 days) for follow-ups. The study flow chart is illustrated in Figure 1.

Figure 1. Study Flow Chart

Protocol GLI.04.US.SL.035

CONFIDENTIAL

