6.3 Inclusion Criteria

The subjects must meet all the following criteria to be eligible for the study:

1. Adult subjects aged 18 years and above
2. Females or males
3. Any Fitzpatrick skin types I-VI, with effort to include $n = 2$ for each category
4. Any races, with effort to include minimum 10% minority ($n = 4$) such as American Indian or Alaska Native, Eastern/Southeastern Asian, South Asians, Black or African American, Native Hawaiian or Other Pacific Islander.
5. Any ethnicities, with effort to include minimum 10% ($n = 4$) of Hispanic, Latino, or Spanish origin
6. Having active target lesion plaques, with minimum area of 2 cm x 2 cm
7. Having mild-to-severe plaque psoriasis with at least 3% Body Surface Area (BSA) and cumulative Target Lesion Severity Score (TLSS) ≥ 6 .
8. Currently on or starting a plaque psoriasis prescription treatment such as biologics, oral or topical therapy for psoriasis, or UV therapy.
9. Subject in general good health
10. Subject willing to stop using current topical skincare products during the duration of the study.
11. Subject willing to replace current skincare products with study products for the duration of the study.
12. For female subjects of childbearing potential, she must not be pregnant, breastfeeding or planning pregnancy during the course of the study. Subjects must be willing to take a urine pregnancy test (UPT) at Baseline visit.
 - Females of non-childbearing potential, e.g., post-menopausal (absence of menstrual bleeding for 1 year without any other medical reason), hysterectomy, or bilateral ovariectomy, are not required to have a UPT.

Protocol Version 02: 29 January 2024

This document contains confidential, proprietary information.

Protocol GLI.04.US.SL.035

CONFIDENTIAL

13. Ability of giving consent for participation in the study
14. Willing to sign a photography release, with minimum 80% of total study panel
15. Agreement to adhere to the procedures and requirements of the study and to report to the site on the day(s) and at the time(s) scheduled for the assessments.

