8.3 Subject Instructions for the Study

Subjects will be provided with the following instruction to follow during the study:

8.3.1. Study Product Usage Instructions:

The study products are used on both face and body:

- *Step 1: Cleanser* – wet skin with lukewarm water, apply the cleanser to wet skin and massage gently. Rinse well and pat dry.
- *Step 2: Moisturizer* – at least twice daily, in the morning and evening, apply the moisturizer liberally to the lesions and all over the body. Reapply the moisturizer as needed throughout the day.
 - If your psoriasis treatment is topical prescription, you can first apply the prescription treatment following its instruction. Wait at least 10 minutes before applying the study moisturizer to the lesions and all over.
- *Step 3: Sunscreen SPF 35* – if you are planning on spending time outdoors, apply the sunscreen to entire face and body before sun exposure once the moisturizers are fully absorbed.

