11.2.2. Local tolerability signs and symptoms (only applicable for cosmetic safety studies)

In cosmetic studies, local skin tolerability includes some expected functional and/or physical signs on the application area, observed by the Investigator or reported by the subjects. Those signs are collected in the final report based on scales or a diary. If the severity of a local skin tolerability sign or symptom, is such that the product application is permanently discontinued and/or a corrective concomitant treatment (except moisturizer or emollient) is prescribed, it is recorded as an undesirable effect (related AE).

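### Tolerability is graded only on target plaques, so treated non-lesional skin has no baseline-referenced grade and disease improvement can hide product irritation

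*Combined protocol and SAP*

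**What the plan says.** Section 11.1 has three graded tolerability items, each scored 0 to 3 with half points allowed: dryness by the investigator, and itching and burning/stinging by the subject. Table 4 names no body site, but the text above it does: "Investigator and subjects will grade the degree of irritation of target lesion areas, at Baseline, Week 2, 4, and 8".

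The area on which the products are used is described in three ways:

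- Section 8.3.1, the subject instructions: "The study products are used on both face and body", and for the moisturizer "apply the moisturizer liberally to the lesions and all over the body". The sunscreen is also for face and body, but only before time outdoors.
- Synopsis, treatment regimen: "apply the study moisturizing cream to the lesion areas". The cleanser step there is not limited to lesions.
- Section 5 (and the synopsis design text): "applying the skincare products to the assigned side of the body based on the pre-determined randomization".

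Table 5 tests the change from Baseline in each tolerability score. It treats a fall, or the absence of a significant rise, as showing that the products are tolerated and safe. Section 4.2 frames the tolerability hypothesis in the same way.

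Section 11.2.2 covers local signs on the application area: "Those signs are collected in the final report based on scales or a diary". It has such a sign recorded as an undesirable effect when product use stops for good or a corrective treatment is prescribed.

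**The concern.** Tolerability is part of the primary objective. The plan measures it in a structured way at one kind of site, and there the scores carry two signals at once. Section 3 describes plaques as itchy and painful. Table 4 defines dryness as roughness, and the upper TLSS scaling grades, an efficacy measure, also refer to a rough surface. Every subject is on prescription psoriasis treatment, which may be newly begun, and there is no control arm. A plaque that improves for any reason lowers the scores meant to reveal irritation, and a subject who scores 3 at Baseline cannot score worse.

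Treated skin without plaques does not carry that disease signal in the same way, yet it has no scale. The study could therefore conclude that a face-and-body regimen is well tolerated from plaque scores that fell because the psoriasis improved, while mild or moderate irritation elsewhere was never graded.

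**Working it through.** The plan gives no power, margin, SD or expected tolerability figure, so there is no stated number to reproduce. The check is mainly a reading of the text, with two pieces of supporting arithmetic.

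**1. Other routes by which non-lesional irritation could be recorded**

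- Adverse events (11, 11.2, 11.2.1, 11.5): questioning at each follow-up visit, with a definition that covers any unfavourable sign or symptom at any site. The set questions ask about health problems and medicine changes. There is no baseline grade.
- Diary (7.6): applications and free comments. Table 5 has no analysis of it.
- DLQI item 1 (Appendix II): itch, soreness, pain and stinging pooled over all skin, at Baseline and Week 8 only. It has a baseline but is not site-specific.
- Self-assessment (Appendix III): cleanser irritation and drying at Week 2, dryness and cracking at Week 4, and cleanser gentleness and a general irritation item at Week 8. There is no baseline. No item asks whether the moisturizer irritates, and none concerns the sunscreen.

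Each route can pick something up. None is both baseline-referenced and specific to treated non-lesional skin.

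**2. Share of treated surface outside plaques, if 8.3.1 governs**

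Non-lesional share = 100% − BSA%. The entry minimum is 3% (inclusion criterion 7), with no cap.

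- BSA 3%: 100 − 3 = 97%
- BSA 10%: 100 − 10 = 90%
- BSA 30%: 100 − 30 = 70%

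It is the majority for any BSA below 50%. The target plaque itself may be as small as 2 cm x 2 cm = 4 cm² (inclusion criterion 6).

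**3. Sensitivity of the plaque scores**

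Inputs from the plan: two-sided 5% test (12.1), 40 to 50 completers (6.1), one-sample t-test (Table 5). The smallest mean rise detectable with 80% power is about (1.960 + 0.842)/√n SDs. That is 2.802/√40 = 0.443 and 2.802/√50 = 0.396. The exact t-test values are 0.454 and 0.404.

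To illustrate masking, assume (these are not in the documents) true irritation of +0.4 point, a disease-related fall of 0, 0.25 or 0.5 point in the same score, and a change SD of 0.6 to 1.0. Net change = 0.4 − fall, and noncentrality = (net change/SD) × √n. At n = 40 and SD 0.8 this gives 0.4/0.8 × 6.325 = 3.16, 0.15/0.8 × 6.325 = 1.19 and −0.1/0.8 × 6.325 = −0.79. Probability of a significant rise at n = 40:

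| Disease-related fall | Net change | SD 0.6 | SD 0.8 | SD 1.0 |
|---|---|---|---|---|
| 0 | +0.40 | 98.4% | 86.9% | 69.4% |
| 0.25 | +0.15 | 33.8% | 21.1% | 15.0% |
| 0.50 | −0.10 | 0.1% | 0.3% | 0.5% |

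At n = 50 and SD 0.8 the three values are 93.4%, 25.5% and 0.2%. Extra subjects within the planned range do not remove the problem.

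**The case against.** The strongest reply is that such irritation is not lost. Section 11.2 has all adverse events reported, requires the investigator to review questionnaire responses and changes in protocol parameters, and has clinically relevant worsening reported whatever its cause. Section 11.2.2 does not say that its threshold overrides those rules. DLQI item 1 and the self-assessment items are not confined to lesions and are tabulated or tested. This stands. A reader might infer that irritation of non-lesional skin goes uncaptured, or that this skin is never assessed. The documents do not support that; what is missing is a systematic grade.

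Second, the whole-body premise rests on 8.3.1, and the synopsis and Section 5 say otherwise. If the synopsis governed, grading lesions would match where the cream goes. This also stands, and it makes the size of the gap conditional. It does not remove the gap: an assigned side of the body would also include non-lesional skin, and the synopsis does not confine the cleanser to lesions.

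Third, grading diseased skin is reasonable in a psoriasis study. Agreed: the plaque scores should stay. The difficulty is in relying on them alone and in how Table 5 reads them.

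Fourth, a TLSS of at least 6 does not mean that the tolerability scores start above zero. TLSS contains no itch or burning item, and erythema 4 + induration 2 + scaling 0 = 6. That is correct, and the point does not rely on it. The number of subjects at the scale ceiling at Baseline is likewise unknown.

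**Conclusion.** The point holds in this form: graded tolerability covers target plaques only, no other source supplies a baseline-referenced grade of treated non-lesional skin, and the Table 5 rule can turn disease improvement into apparent product tolerability. It warrants a change to the plan but does not invalidate the study.

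The 97% applies only to whole-body use at the entry minimum. It is a share of surface, and reading it as a rate of missed irritation would go beyond the documents, which give no irritation rates. The masking probabilities rest on an assumed effect, assumed disease-related falls and assumed SDs, and on a t-test applied to a short ordinal scale. They show the mechanism and its direction, not an expected result. That plaque itch and roughness vary with the disease follows from the plan's own descriptions in Section 3, Table 2 and Table 4.

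**What to change.** 1. Reconcile the treated area across the synopsis, Section 5 and Section 8.3.1. The sponsor must settle which text applies; the tolerability change should follow that decision and not pre-empt it.
2. For whatever non-lesional skin is treated under the reconciled text, add to 11.1 and Table 4 the same three items, by the same raters, at Baseline and Weeks 2, 4 and 8. Use a pre-specified non-lesional site fixed at Baseline. A worst-area rule could compare different sites at different visits.
3. Add a separate Table 5 row for these scores: number of subjects at each grade and number worsening by at least 1 point from Baseline.
4. State in Table 5 that a fall, or no rise, in target-lesion scores also reflects disease activity and does not by itself show product tolerability.

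The cost is three extra scores per visit, a CRF addition, one more table and a little visit time, with no new visits or equipment. The tolerability figure may come out less favourable. The added row does not remove disease confounding from the plaque scores, and the comparison remains single-arm, which is why item 4 is needed as well.

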11.2 Adverse Events

Throughout the course of the study, all adverse events will be monitored and reported on an adverse event CRF/eCRF without omitting any requested and known information. When AEs occur, the main concern is the safety of the study subjects. At time of the informed consent signature, each subject must be given the name and phone number of investigational site personnel for reporting AEs and medical emergencies.

At each visit, after the subject has had the opportunity to spontaneously mention any problems, the Investigator should inquire about AEs by asking the standard questions:

- “Have you had any health problems since your last study visit?”
- “Have there been any changes in the medicines you take since your last study visit?”

Protocol Version 02: 29 January 2024

This document contains confidential, proprietary information.

Protocol GLI.04.US.SL.035

CONFIDENTIAL

AEs should be reported for any clinically relevant change, as determined by the Investigator, in concomitant medication(s) that is the result of an untoward (unfavorable and unintended) change from baseline in a subject's medical health following exposure to the study treatment.

Changes from baseline in any protocol-specific parameter evaluated during the study are to be reviewed by the Investigator. In addition, the subject's responses to any questionnaire utilized during the study are to be reviewed by the Investigator. Any untoward (unfavorable and unintended) change from baseline in a protocol-specific parameter or question response that is clinically relevant, in the opinion of the Investigator, is to be reported as an AE. These clinically relevant changes will be reported regardless of causality.

11.2.1. Definition of an Adverse Event

An adverse event (AE) is defined as any untoward medical occurrence in a subject taking part in the clinical study, and which does not necessarily require a causal relationship with the investigational product and/or a clinical trial procedure.

An AE can be any unfavourable and unintended sign (including an abnormal laboratory value), symptom, or disease temporally associated with the use of the investigational product, whether or not related to this product.

When an AE has a likely or very likely causal relationship with the investigational product and/or a clinical trial procedure, it is named related AE.

11.2.2. Local tolerability signs and symptoms (only applicable for cosmetic safety studies)

In cosmetic studies, local skin tolerability includes some expected functional and/or physical signs on the application area, observed by the Investigator or reported by the subjects. Those signs are collected in the final report based on scales or a diary. If the severity of a local skin tolerability sign or symptom, is such that the product application is permanently discontinued and/or a corrective concomitant treatment (except moisturizer or emollient) is prescribed, it is recorded as an undesirable effect (related AE).

11.2.3. Definition of a Serious Adverse Event (SAE) and serious undesirable effect/related SAE

A serious adverse event (SAE) means an adverse event that results in:

- i. death;
- ii. a life-threatening experience;
- iii. inpatient hospitalization;
- iv. a persistent or significant disability or incapacity;
- v. a congenital anomaly or birth defect;
- vi. an infection; or
- vii. significant disfigurement (including serious and persistent rashes, second- or third-degree burns, significant hair loss, or persistent or significant alteration of

Protocol GLI.04.US.SL.035

CONFIDENTIAL

appearance), other than as intended, under conditions of use that are customary or usual.

Notes:

The term “immediate vital risk” refers to an event in which the subject was at risk of death at the time of the event; it does not refer to an event that hypothetically might have caused death if it was more severe.

Inpatient hospitalization is considered to have occurred if the subject has had to stay for a night at the hospital. Hospitalization solely for the purpose of a diagnostic test (even if related to an AE), elective hospitalization for an intervention that was already planned before subject enrolment in the clinical trial, admission to a day-care facility, social admission (e.g., if the subject has no place to sleep), or administrative admission (e.g., for a yearly examination) should not be considered as a SAE.

A serious related SAE is defined as any SAE which the Investigator classifies as having a reasonable possibility for a causal relationship with the investigational product and/or the clinical trial procedure.

